Mirabegron has binding K_is for the human β 1-, β 2-, and β 3-adrenergic receptors of 4200, 1300, and 40 nM, respectively. These values demonstrate a much greater β 3-AR selectivity compared with pindolol, making mirabegron a promising candidate for adipose tissue-specific activation. In males, for 50 mg, the C_{max} and T_{max} were 23.7 ng/mL and 3.50 h, respectively, and for 200 mg, the C_{max} and T_{max} were 158 ng/mL and 2.68 h, respectively (FDA 2012). In our experience, as will be described in detail below, the C_{max} for a 200 mg dose was 274 ± 64 nM based on 65% protein binding, which is 6.9x the K_i of mirabegron for the β 3-AR (40 nM). If the 50 mg dose achieves 18% of

200 mg, then the C_{max} would be 49 nM, which is 1.2x the K_i and 2.2x the in vitro EC_{50} of 22.4 nM (Takasu et al., 2007).

We have recently completed a pilot study of the effectiveness of a one-time dose mirabegron 200 mg to stimulate human BAT and increase energy expenditure in young (22.2 ± 0.6 years), lean (22.7 ± 0.5 kg/m 2), healthy men who were already known to have detectable BAT via PET/CT. The pilot study achieved its primary endpoint by demonstrating that mirabegron at 200mg significantly stimulated BAT metabolic activity and led to a 13% increase in RMR, demonstrating that a β 3-AR agonist can stimulate human BAT thermogenesis and may be a promising treatment for metabolic disease.

The principal limitation of the pilot study is that the dose used (200mg) was higher than the approved dose of 50mg, and this difference was associated with clinically relevant adverse effects. At 3.5 hours after dosing with 200mg mirabegron, we observed increases in mean HR (14 ± 3 bpm) and systolic BP (11 ± 2 mmHg), but not diastolic BP (2 ± 1 mmHg). This is consistent with information provided in the Background Document for Meeting of Advisory Committee for Reproductive Health Drugs (FDA 2012); although, a slightly higher increase in diastolic blood pressure (+7.7 mm Hg) was reported by the FDA, which is greater than our previous experience with a 200 mg dose of the drug. These treatment-emergent adverse effects are thought to be a result of off-target binding of the drug to β 1-ARs ([name] 2015). Although very promising, these preliminary results indicate that mirabegron will not be useful clinically unless the cardiovascular stimulation can be limited while still stimulating NST and BAT.

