To conduct future studies of mirabegron-induced NST, we will need to determine the optimal dosing strategy for mirabegron. In the first phase of this sub-study, we will perform a dose-response analysis of mirabegron at 0mg, 50mg, and 200mg, using mild cold exposure as a positive control. Should the 50mg dosage be sufficiently effective, this dose will be used in subsequent studies. If not, we will consider a second sub-study in which mirabegron will be combined with a selective β 1-AR blocker, likely choosing pindolol or nebivolol.

Of note, the study will continue the use of pindolol in Cohort 1 (as described above). There are at least two reasons we have chosen to do so. First, its mechanism of action is quite different from mirabegron. It can serve as a negative control for β 3-AR binding while having β 1 and β 2 binding. Second, 8 subjects (as of January, 2015) have already taken pindolol as part of Cohort 1, so it would be important to continue until the planned interim/final analysis before deciding to terminate its use early.

I.3 Assaying anti-obesity drugs for their effects on EE

Significance of improving assay of drugs that stimulate EE

When studied in detail in mice, it appears that the vast majority of centrally-acting drugs have dual beneficial effects of decreasing food intake and increasing metabolic rate^{60,61}. Despite of the huge magnitude of facultative thermogenesis in mice, care is not always being taken to test drugs for metabolic effects at thermoneutrality.⁶² While the effect of environmental temperature on metabolic rate was first described by Lavoisier in 1790⁶³, studies of drug effect on EE in humans have not always rigorously enforced the

use of thermoneutral conditions. We propose to first explicitly demonstrate the need for measuring drug effect under thermoneutral conditions and then re-evaluate the effect of anti-obesity drugs on BMR employing our new knowledge of human capacity for NST under our optimized experimental conditions.

Caffeine

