- 1) Propranolol 160 mg PO will reduce the resting EE measured at a temperature just above the subject's placebo shivering threshold (REE_{Low}) by greater than or equal to 5% compared to placebo REE_{Low} . If propranolol-treated subjects shiver at the low temperature, then measurement of non-shivering EE is not possible in this protocol. Propranolol will be judged to increase the shivering threshold if significantly more subjects shiver with propranolol than with placebo treatment.
- 2) Pindolol 20 mg PO will lead to a similar difference in resting EE measured at thermoneutrality ($REE_{27^\circ C}$) and REE_{Low} .
- 3) Dantrolene 100 mg PO will reduce the REE_{Low} by greater than or equal to 5% compared to placebo REE_{Low} . If dantrolene-treated subjects shiver at the low temperature, then measurement of non-shivering EE is not possible in this protocol. Dantrolene will be judged to increase the shivering threshold if significantly more subjects shiver with dantrolene than with placebo treatment.
- 4) Magnesium sulfate (50 mg/kg bolus followed maintenance infusion at 2 g/h) will reduce the REE_{Low} by greater than or equal to 5% compared to REE_{Low} .

Cohort 2

- 1) To evaluate the effect of caffeine (300 mg PO) on BMR ($=REE_{27^\circ C}$).
- 2) To evaluate the effect of Qsymia (topiramate 92 mg CR, phentermine 15 mg PO) on BMR.

- 3) To evaluate the effect of phentermine (37.5 mg PO) on BMR.
- 4) To evaluate the effect of topiramate (200 mg PO) on BMR.
- 5) To evaluate the effect of naltrexone (100 mg PO) on BMR.

Hypotheses

- 1) Caffeine 300 mg PO will increase BMR by greater than or equal to 5% vs placebo.
- 2) Qsymia (topiramate 92 mg CR, phentermine 15 mg) PO will increase BMR by greater than or equal to 5% vs placebo.
- 3) Phentermine 37.5 mg PO will increase BMR by greater than or equal to 5% vs placebo.
- 4) Topiramate 200 mg PO will increase BMR by greater than or equal to 5% vs placebo.
- 5) Naltrexone 100 mg PO will increase BMR by greater than or equal to 5% vs placebo.

Cohort 3 – This Cohort has completed enrollment

- 1) To compare the effects of mirabegron at 0mg, 50mg, and 200mg on BAT metabolic activity.
- 2) To compare the effects of mirabegron at 0mg, 50mg, and 200mg on BMR.

Hypotheses

- 1) Mirabegron at 50mg and 200mg PO will each increase BMR and BAT activity more than placebo.
- 2) The increases in heart rate and systolic BP after a one-time dose of 50mg will be lower than that observed using 200mg.

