Power calculation: To estimate power, we used data from 12-DK-0097. We first determined that the within-subject difference in the response in BMR within TNZ was normally distributed with a standard deviation of 2.54%. The maximum NST in 9 young healthy male subjects was $17.4 \pm 3.7\%$. With 12 subjects completing the protocol, if the true difference in the mean response to treatment is 5.0% as we hypothesized for each drug treatment, we will be able to reject the null hypothesis that this response difference is zero with probability (power) of 0.98 at an alpha of 0.05 in either Cohort. Since this study is designed to use the pharmacological agents only to test the mechanisms of NST and BMR, thus we will not compare any pharmacological interventions to each other. However, in the most conservative interpretation, multiple comparisons adjustments will only be necessary for the number of paired comparisons between drugs and placebo within each Cohort. The result of such a conservative estimate of power range from 0.92 at an alpha value of 0.01 (0.05/5, the Bonferroni method) in Cohort 2 to 0.94 in Cohort 1 (alpha = 0.05/4). Even if the true difference was 3%, the power to detect with n=12 is above 0.83 in all analyses. To consider in potential dropouts (about 30%), we will recruit 16 subjects for each cohort (subjects can participate in both with a minimum of 2 weeks washout in between the studies), aiming to have 12 completers for each cohort.

In Cohort 3, the primary endpoint is the difference in detectable BAT activity (units of $\text{mL}^* \text{SUVmean}^* \text{g/mL}$) between the 0 mg and 50 mg doses of mirabegron. Based on our previous study ([name] et al., 2015), BAT activity is right-skewed and not

normally distributed, so our sample size determination is based on log BAT activity, which is normally distributed. We found that log BAT activity after treatment with 0 mg mirabegron was 0.05 ± 0.62 and after treatment with 200 mg mirabegron was 2.00 ± 0.79 . Since it is unknown what the effect of 50 mg mirabegron would be on BAT activity, we calculated a range based on lower and upper bound expectations about the reported PK/PD profile of mirabegron. For the lower bound, the 50 mg dose has been found to have a mean plasma C_{max} that is 18% of 200 mg. If there were a linear relationship between BAT activity and dose, then we would predict 50 mg to produce a mean log BAT activity of 0.36.

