Using a different set of assumptions leads to a higher predicted effect, or the upper bound expectation. We found that after the 200 mg dose, the estimated mean peak plasma concentration (C_{max}) of mirabegron was 274 ± 64 nM based on 65% protein binding, which is 6.9x the K_i of mirabegron for the $\beta 3$ -AR (40 nM) (FDA 2012). If the 50 mg dose achieves 18% of 200 mg, then the C_{max} would be 49 nM, which is 1.2x the K_i and 2.2x the in vitro EC_{50} of 22.4 nM (Takasu et al., 2007). Therefore, 50 mg mirabegron could produce $\geq 50\%$ of the effect seen with 200 mg, or ≥ 1.00 log BAT activity. Therefore, for 50 mg mirabegron, the effect on log BAT activity ranges from 0.36 to ≥ 1.00 .

For sample standard deviation, the log BAT activity after treatment with 0 mg mirabegron was 0.05 ± 0.62 and after treatment with 200 mg mirabegron was 2.00 ± 0.79 . Assuming a linear relationship between dose and standard deviation of the outcome variable, for the 50 mg dose of mirabegron, the standard deviation for log BAT activity is predicted to be 0.66.

In summary, we are planning a study of a continuous response variable from study subjects where each acts as his own paired control. Assuming the true difference between 0 mg mirabegron and 50 mg mirabegron is 0.36 with a standard deviation of 0.66, we will need to study 28 subjects to be able to reject the null hypothesis that this response difference is 0 with $\alpha=0.05$ and power of 80%. However, if the response is 1.00, then we will need to study only 6 subjects. Given this wide range (6-28 subjects), we will plan to complete 28 subjects with an interim analysis after 12 subjects. If the results of the interim analysis suggest that the response is closer to the upper bound estimate, then we will be able to reject our null hypothesis at that point. A sample size of 12 was chosen because if 12/12 subjects show higher BAT activity with the 50 mg, then non-parametric paired comparison yields a P value of 0.001.

For these types of studies, we have experienced a screen-failure rate of 50% and a rate of detectable BAT of 66%. We therefore plan to enroll up to 84 subjects, perform Study Day A in 42, and expect 28 to complete all four study days. If we are able to complete the study after the interim analysis, then we would end up enrolling 36 subjects, initiate the screening protocol with 18, and have 12 complete all four study days.

III.2-1 Protocol design, Cohort 1 – This Cohort has completed enrollment

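### Cohort 3 compares heart rate and systolic BP at 50 mg mirabegron only with 200 mg, and the sentence on carrying 50 mg forward names effectiveness alone, so neither shows whether cardiovascular stimulation at 50 mg is small

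*Combined protocol and SAP*

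**What the plan says.** Four places bear on this point.

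- **Section I.2, Mirabegron, on the pilot.** At 200 mg, "we observed increases in mean HR (14 ± 3 bpm) and systolic BP (11 ± 2 mmHg". From this the protocol concludes that "mirabegron will not be useful clinically unless the cardiovascular stimulation can be limited while still stimulating NST and BAT".
- **Section I.2, Mirabegron, on the next step.** "Should the 50mg dosage be sufficiently effective, this dose will be used in subsequent studies". A second sub-study, adding a β1 blocker, is to be considered only if 50 mg is not effective enough. Effective enough is not defined, and no heart-rate or BP condition appears.
- **Section II.1, Cohort 3 hypotheses.** Hypothesis 1 uses placebo as comparator: "Mirabegron at 50mg and 200mg PO will each increase BMR and BAT activity more than placebo". Hypothesis 2 uses 200 mg: "The increases in heart rate and systolic BP after a one-time dose of 50mg will be lower than that observed using 200mg".
- **Sections II.3, III.2-3 and III.5.** Subjects with detectable BAT receive 0, 50 and 200 mg in randomised order. Heart rate is recorded by Holter monitor in the chamber and is listed as an exploratory outcome, with no comparator or limit.

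The text gives no 50 mg vs 0 mg cardiovascular contrast and no ceiling on the rise.

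**The concern.** The protocol sets two conditions for usefulness: the BAT effect stays, and cardiovascular stimulation is limited. The BAT side is tested against placebo. The cardiovascular side is tested only against a dose that the pilot had already found to have clinically relevant adverse effects. A rise that is lower than at 200 mg may still be of any size below 14 bpm or 11 mmHg. The carry-forward sentence does not look at heart rate or BP at all.

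The stake is that hypotheses 1 and 2 could both be met, and 50 mg used in later studies, without an estimate of what 50 mg does to heart rate and BP relative to no drug. The question is relevant to this dose: section III.6 lists raised blood pressure (9–11%) and raised heart rate (2%) with chronic use at 50 mg. No placebo rates are given there, so this shows relevance and not size.

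**Working it through.** **The plan's own figure.** Section III.1 gives 28 subjects for a paired difference of 0.36 in log BAT activity, SD 0.66, alpha 0.05, power 80%. I take the test as two-sided, which is not stated. The normal approximation gives (0.66 × (1.960 + 0.842) / 0.36)² = 26.4, so 27; the paired t-test gives 29. For a difference of 1.00 the t-test gives 6, as stated. The figures reproduce, but they cover BAT activity only. No sample-size figure is given for heart rate or BP.

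**Step 1: exposure.** The Cmax values for men in section I.2 give 23.7/158 = 0.15. Section III.1 says "the 50 mg dose has been found to have a mean plasma C_{max} that is 18% of 200 mg". The range is 15–18%.

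**Step 2: what each contrast can show.** The pilot values after the ± sign are not labelled SD or SEM, and the pilot n is not given. I use SD 3 bpm (read as SD) and 3 × √12 = 10.4 bpm (read as SEM with an assumed n of 12), applied to the paired difference in a two-sided paired t-test at 0.05. Exposure scaling gives a rise of 0.18 × 14 = 2.5 bpm. The 7 bpm row is an assumption, half of 14.

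| True heart-rate rise at 50 mg | n | Power, 50 vs 200 mg | Power, 50 vs 0 mg |
|---|---|---|---|
| 2.5 bpm | 12 | 0.94 to about 1 | 0.12 to 0.76 |
| 2.5 bpm | 28 | about 1 | 0.24 to 0.99 |
| 7 bpm | 12 | 0.57 to about 1 | 0.57 to about 1 |
| 7 bpm | 28 | 0.93 to about 1 | 0.93 to about 1 |

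At 28 subjects hypothesis 2 is met with high power whether the true rise is 2.5 or 7 bpm. It therefore cannot separate the two cases.

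**Step 3: the BAT-to-heart ratio.** Section III.1 reports "log BAT activity after treatment with 0 mg mirabegron was 0.05 ± 0.62 and after treatment with 200 mg mirabegron was 2.00 ± 0.79", a gain of 2.00 − 0.05 = 1.95. It adds that "for 50 mg mirabegron, the effect on log BAT activity ranges from 0.36 to" at least 1.00, so the gain at 50 mg runs from 0.36 − 0.05 = 0.31 to 1.00 − 0.05 = 0.95. The ratio at 50 mg is worse than at 200 mg when the rise exceeds (rise at 200 mg) × (gain at 50 mg) / 1.95:

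- Lower bound, heart rate: 14 × 0.31/1.95 = 2.2 bpm.
- Lower bound, systolic BP: 11 × 0.31/1.95 = 1.7 mmHg.
- Upper bound, heart rate: 14 × 0.95/1.95 = 6.8 bpm.
- Upper bound, systolic BP: 11 × 0.95/1.95 = 5.4 mmHg.

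All four lie below the 200 mg rises, so hypothesis 2 can be met on either side of them.

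**Step 4: receptor occupancy.** Simple occupancy is C/(C + Ki), with Ki of 40 nM (β3) and 4200 nM (β1) and the stated free concentrations of 274 and 49 nM.

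- β3: 274/314 = 0.873 at 200 mg and 49/89 = 0.551 at 50 mg, so 63% is retained.
- β1: 274/4474 = 0.061 at 200 mg and 49/4249 = 0.0115 at 50 mg, so 19% is retained.

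On this calculation 50 mg is the more selective dose.

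**The case against.** A reader might infer that the plan steers towards a dose less selective than 200 mg. The documents do not support that. The inference needs a large cardiovascular effect at 50 mg, such as half of that at 200 mg, paired with a BAT effect scaled to exposure (0.31/1.95 = 16%). That mixes two models. With exposure scaling on both sides, about 18% of the heart-rate rise goes with 16–18% of the BAT gain, and the ratios are about equal. The protocol attributes the cardiovascular effects to off-target β1 binding, and occupancy then favours 50 mg. This part of the objection stands.

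A reader might also infer that the dose decision turns on hypothesis 2. It does not: the carry-forward sentence uses no cardiovascular result. Nor is hypothesis 2 certain to be met. With a 7 bpm rise and the wider SD, power at the interim size of 12 is 0.57 for heart rate, and 0.71 for systolic BP with a 5.5 mmHg rise and SD 2 × √12 = 6.9.

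The increases in hypothesis 2 may be meant relative to placebo, as section I.2 does when it reports the FDA figures. That does not change the contrast: (50 − 0) − (200 − 0) = 50 − 200, so the 0 mg value cancels.

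Finally, the 0 mg data and the heart-rate recording are there, and Cohort 3 has completed enrolment. Both are true. They make the repair one of analysis and reporting.

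**Conclusion.** The point holds in a limited form. The protocol's condition that cardiovascular stimulation be limited is not addressed by hypothesis 2, which compares 50 mg with 200 mg only, nor by the carry-forward sentence, which names effectiveness only. With exposure at 15–18%, a smaller rise than at 200 mg is likely and says little about its size at 50 mg.

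This describes what the plan leaves untested. It does not predict a worse ratio at 50 mg: the break-even heart-rate rise is about 2.2 bpm at the lower BAT bound and 6.8 bpm at the upper bound. The power figures rest on an assumed SD of 3 to 10.4 bpm. The break-even rises use the plan's log scale, whose base is not stated. On that scale the lower bound keeps 16% of the 200 mg gain; after back-transforming it keeps about 6% (natural log) or 1% (base 10). The ratio is therefore not a stable basis for a decision.

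**What to change.** 1. In Cohort 3 hypothesis 2, make the cardiovascular contrasts 50 mg vs 0 mg and 200 mg vs 0 mg, within subject and at a matched post-dose time, for heart rate and systolic BP. Report estimates with confidence intervals. Keep 50 vs 200 mg as supportive.
2. State that a non-significant 50 vs 0 mg result will not be read as no effect. The interval shows which rises remain compatible with the data.
3. Reconcile the carry-forward sentence in section I.2 with the protocol's own statement, in the same section, that cardiovascular stimulation must be limited as well. Any limit is for the sponsor to set.

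The cost is mainly wording and a few added estimates. The 0 mg day and heart-rate recording are already in the design, and hypothesis 2 already needs systolic BP. The readable text gives no in-chamber BP schedule for Cohort 3 (Figure 2 is not shown), so the sponsor should confirm that matched times exist. If Cohort 3 results have already been seen, label the contrasts as added afterwards. The small downside is imprecision: for exposure-scaled heart-rate rises, 50 vs 0 mg has power of only 0.12 to 0.76 at 12 subjects and 0.24 to 0.99 at 28.

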Caffeine has been chosen as the reference drug (positive control) for studying an increase in EE. Caffeine has multiple pharmacologic actions, with its effects at modest doses in humans being attributed to antagonism of the A₁R and A_{2A}R adenosine receptors ⁶⁴. Caffeine was first shown to increase EE by Hoppe in 1857 (see ⁶⁵) and has been studied many times since. In an analysis of 12 studies using doses from 50 to 536 mg (published between 1915 and 2008 ⁶⁶⁻⁷⁷) there was an approximately linear increase in EE with caffeine dose, with ~10% increase at a dose of 300 mg.

Caffeine is completely absorbed, with a Cmax of ~0.5 hours and a t_{1/2} of ~4-6 hours with multiple active metabolites ⁶⁴. Notably, there is attenuation of pharmacodynamic responses to caffeine with repeated dosing, which is avoided by keeping at least 72 hours between doses ^{78,79}. Possible adverse reactions are: frequent passing of urine, nervousness, restlessness, diarrhea, headache, and stomach upset. We propose dosing 300 mg caffeine, which is the same amount as in the Starbucks Grande size (<http://www.cspinet.org/new/cafchart.htm>). Actions of caffeine include some increase in blood pressure and heart rate ⁷⁸ and increased alertness and reduced fatigue ⁸⁰.

300 mg caffeine is predicted to increase EE at thermoneutrality by at least 10% (the effect will be larger if the prior studies were underestimations due to not using thermoneutral conditions). The effect on BMR by caffeine will serve as a positive control for the potential effects by other anti-obesity drugs.

Phentermine

Phentermine is a sympathomimetic drug approved for the short-term treatment of obesity (Adipex-P label:

http://www.accessdata.fda.gov/drugsatfda_docs/label/2012/085128s065lbl.pdf). The dose of 37.5 mg daily (30 mg free base) is twice the amount in the recently approved drug Qsymia (see below). The only publication known to us reporting the effect of phentermine on EE was of a 1.4% non-significant increase in resting metabolic rate with 8 mg TID x 5 days ⁸¹. Phentermine has a Cmax at 2-4 hours and a t_{1/2} of 19 ±4 hours. These pharmacokinetics suggest that 4 days should be allowed after dosing for drug to be adequately cleared.

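### Cohorts 1 and 2 name only unadjusted 0.05 and single-step Bonferroni; Holm keeps the same familywise bound, is never less powerful, and needs no extra subjects

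*Combined protocol and SAP*

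**What the plan says.** The power paragraph (III.1, Subjects and Recruitment) plans on 12 completers per cohort: "With 12 subjects completing the protocol, if the true difference in the mean response to treatment is 5.0"%, the test would "reject the null hypothesis that this response difference is zero" with "probability (power) of 0.98 at an alpha of 0.05 in either Cohort". The variability input is described as "normally distributed with a standard deviation of 2.54"%.

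On multiplicity, the paragraph says that "in the most conservative interpretation, multiple comparisons adjustments will only be necessary for the number of paired comparisons between drugs and placebo within each Cohort". It then gives power of 0.92 at "an alpha value of 0.01 (0.05/5, the Bonferroni method) in Cohort 2" and 0.94 at 0.05/4 in Cohort 1, and says that power for a 3% difference stays above 0.83 in all analyses. It names no other procedure for these two cohorts, and no analysis section commits to adjusted or unadjusted testing.

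The Cohort 2 family of five is caffeine, Qsymia, phentermine, topiramate and naltrexone, each with its own primary objective and hypothesis against placebo (II.1). Caffeine has a second role in I.3: "The effect on BMR by caffeine will serve as a positive control for the potential effects by other anti-obesity drugs", with a predicted increase of at least 10%. In Cohort 1, three hypotheses predict a reduction in cold-temperature expenditure (propranolol, dantrolene, magnesium). The pindolol hypothesis instead predicts similarity. Cohorts 1 and 3 are marked as fully enrolled; Cohort 2 is not.

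**The concern.** The two options on the page are both weaker than they need to be. Unadjusted testing at 0.05 does not control the chance of a false claim across several drugs that share one placebo measurement. Single-step Bonferroni controls it, but holds every drug to the strictest threshold even after others have been rejected. Holm gives the same control under any dependence between the tests and relaxes the threshold step by step, so it can only add rejections.

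At stake is the chance of detecting a modest effect of a Cohort 2 drug with only 12 completers. Because neither option is committed to, the threshold could also be chosen between 0.05 and 0.01 after the results are seen.

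**Working it through.** **Inputs.** From III.1: n = 12; differences of 5% and 3%; SD 2.54%; alpha 0.05, 0.05/4 = 0.0125 and 0.05/5 = 0.01. From I.3: caffeine +10%. Assumptions: two-sided paired t-tests (the null is a zero difference, but sidedness is not stated), and equal variances, so that sharing one placebo day gives a correlation of 0.5 between drug-placebo differences.

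The plan does not make clear whether 2.54% is the SD of one measurement or of the paired difference. Both readings are carried: SD of the difference 2.54%, or 2.54 × √2 = 3.59%.

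**1. The plan's own power figures.** Power comes from the noncentral t with 11 df and noncentrality δ√12/SD. For example, 5 × 3.464/3.59 = 4.82, against a critical value of 3.106 at alpha 0.01.

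| Effect | SD of difference | alpha 0.05 | 0.0125 | 0.01 |
|---|---|---|---|---|
| 5%, as stated | – | 0.98 | 0.94 | 0.92 |
| 5% | 2.54 | 1.000 | 0.999 | 0.999 |
| 5% | 3.59 | 0.992 | 0.946 | 0.931 |
| 5% | 3.7 | 0.989 | 0.932 | 0.915 |
| 3%, as stated | – | above 0.83 | above 0.83 | above 0.83 |
| 3% | 2.54 | 0.96 | 0.84 | 0.81 |
| 3% | 3.59 | 0.75 | 0.50 | 0.45 |

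The 5% figures fit an SD of about 3.6 to 3.7 (the paragraph's other spread figure is 3.7). The 3% sentence nearly fits 2.54. No single SD gives both, so the gain must be shown for a range.

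**2. Familywise error without adjustment.** Independent tests would give 1 − 0.95⁵ = 0.226 for five nulls and 1 − 0.95⁴ = 0.185 for four. With the shared placebo day, simulation (at least 40,000 trials per scenario) gives about 0.19 with all five null, and about 0.16 over the other four when caffeine works. Holm over five stayed below 0.05 in every configuration with true nulls.

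**3. Bonferroni against Holm in Cohort 2.** Holm compares the ordered p-values with 0.05/5, 0.05/4, 0.05/3, 0.05/2 and 0.05 (0.01, 0.0125, 0.0167, 0.025, 0.05), stopping at the first failure. Power per non-caffeine drug, with caffeine at +10%:

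| Truly active besides caffeine | Effect | SD | Bonferroni | Holm |
|---|---|---|---|---|
| all four | 3% | 2.54 | 0.81 | 0.93 |
| all four | 3% | 3.59 | 0.45 | 0.61 |
| all four | 5% | 3.59 | 0.93 | 0.99 |
| one only | 3% | 2.54 | 0.81 | 0.84 |
| one only | 3% | 3.59 | 0.45 | 0.50 |
| one only | 5% | 3.59 | 0.93 | 0.95 |

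At 5% with SD 2.54, Bonferroni is already at 0.999. The chance of at least one rejection in the family is identical under the two methods, because both start at 0.01.

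**4. Testing caffeine outside the family.** When caffeine has its predicted effect, Holm over five and Holm over the other four give the same power for those four (0.928 for both at 3%, SD 2.54). If caffeine were tested separately at 0.05 and Holm run over the remaining four, familywise error over the five primary tests would be about 0.086 with all null, against about 0.044 for Holm over five.

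**The case against.** The strongest reply is that Bonferroni is not the planned analysis. It appears as a conservative bound inside a power calculation whose headline uses 0.05. That is right: a reader might infer that the trial will lose power to Bonferroni, but the documents do not commit to it. Against unadjusted testing Holm lowers power slightly (0.96 to 0.93 at 3%, SD 2.54); what it buys there is error control. The comparison with Bonferroni matters because Bonferroni is the only adjustment on offer.

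The second reply is that gains of 12 to 16 points require every drug to work. This also stands. All drugs at 5% is the plan's planning assumption, but I.3 is less confident. It cites non-significant increases of 1.4% for phentermine and 4.6% for naltrexone, reports no study of Qsymia, and located none of single-dose topiramate. With one other active drug the gain is 2 to 4 points.

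A reader might also infer that counting the positive control among the five tests is a mistake. The documents do not support that: caffeine is the first Cohort 2 primary objective. Removing it would nearly double the familywise error when all five are null, and adds no power beyond Holm when caffeine works. Nor is the plan silent on assay sensitivity, since I.3 states caffeine's role; only an explicit reporting rule is absent.

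Finally, Cohort 1 cannot be treated as four ordinary superiority tests. Rejecting a zero difference for pindolol could count against its hypothesis.

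**Conclusion.** The point holds as a choice of method. Holm gives the same 0.05 familywise bound as the only adjustment named, with the same 12 completers, and is never less powerful. In Cohort 2 the gain per drug is about 6 to 16 points if all four non-caffeine drugs work (except at 5% with SD 2.54%), about 2 to 4 points if one does, and nil at 5% if 2.54% is truly the SD of the paired difference. Leaving the tests unadjusted carries a familywise error of about 0.16 to 0.19, depending on whether caffeine works.

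The power and error sizes rest on two-sided paired t-tests, a correlation of 0.5 from the shared placebo day, and the SD range above. Holm's error bound and its advantage over Bonferroni do not depend on those assumptions, provided that the individual p-values are valid. The point does not show that the plan commits to Bonferroni or that caffeine is wrongly counted.

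**What to change.** In the III.1 power paragraph, replace the Bonferroni wording with a commitment made before Cohort 2 is analysed: Holm step-down at two-sided familywise 0.05 over all five Cohort 2 drug-placebo comparisons, caffeine included.

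For Cohort 1, apply Holm at familywise 0.05 to the three reduction hypotheses (propranolol, dantrolene, magnesium), and state separately how pindolol's similarity hypothesis will be assessed. As that cohort is fully enrolled, date the change and say whether its data had been seen.

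State whether 2.54% is the SD of one measurement or of the paired difference, so that the power figures can be restated on one basis.

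Optionally, add that a non-significant result for another Cohort 2 drug will be reported as no detectable effect only if caffeine is significant; otherwise the assay will be reported as not shown to be sensitive.

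The cost is a few sentences, with no added subjects, visits or data. One small drawback is that Holm has no simple matching simultaneous confidence intervals, so unadjusted 95% intervals should be reported, labelled as such, beside the Holm-adjusted p-values.
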